9.4.7. Exploratory Endpoints

As exploratory analyses, the primary and secondary analyses may be repeated on the Treatment populations and on all participants who are in either the Prevention or Treatment populations in Part 1 and 2.

Additional exploratory analyses for Part 1 and Part 2 may include

- time to improvement of COVID-19 disease to mild severity, in the subset of the participants who have at baseline, or develop, moderate or worse COVID-19
- worst score according to NIAID ordinal scale(s)
- examination of virology for participants who become SARS-CoV-2 positive,
- examination of viral resistance to each study intervention,
- duration of hospitalization in participants who are hospitalized due to COVID-19, and
- subgroup analyses of primary and key secondary endpoints within residents versus staff.

For Part 3, exploratory analyses are listed in Section 3.

Additional exploratory analyses on Part 3 may be conducted.

Details on these analyses will be described in the SAP.

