## **5.2. Determination of Sample Size**

For Part 1, an estimated 33 events are needed to show superiority of LY3819253-4200mg over placebo in each of the primary and key secondary endpoints, using the formula by Schoenfeld (1983). An average sample size of approximately 1300 participants who are SARS-CoV-2 PCR negative and serology negative at baseline is expected to obtain the needed number of events for each endpoint.

For Part 2, an estimated 56 events in the Prevention Cohort are needed to show superiority over placebo for either LY3819253-700mg or LY3819253-350mg+LY3832479-700mg in each of the primary and key secondary endpoints. Approximately 2000 participants on average will be randomly assigned to study intervention such that approximately 1700 participants are randomized in the Prevention Cohort with the goal of achieving approximately 56 events on each of the primary and key secondary endpoints.

The maximum sample size for this study is approximately 5000 participants in the intent-to-treat (ITT) population.

Participants will be residents and staff of skilled nursing and assisted living facilities. Globally, there are many reports of the rapid spread of COVID-19 amongst residents of skilled nursing facilities following identification of an index case, with high associated rates of morbidity and mortality (Arons et al. 2020; Grabowski). Given that residents at these facilities are at higher risk for having a more severe disease course of COVID-19, this will be an important population to participate in the study. Therefore, a minimum of 300 residents will be enrolled.

Operationally, this will be accomplished, when possible, by identifying facilities where approximately half of the participants interested in the study are residents.

For sample size determination for Part 1, the following assumptions were used:

- 1) two-sided significance level of 0.05;
- 2) 90% power for the primary and key secondary endpoints;
- 3) an 8-week placebo group event rate of 4.0% for moderate or worse severity COVID-19;
- 4) a risk ratio of 0.33 between LY3819253 and placebo in terms of the primary and key secondary endpoints.

For sample size determination for Part 2, the following assumptions were used:

- 1) two-sided significance level of 0.025;
- 2) 90% power for the primary and key secondary endpoints;
- 3) an 8-week placebo group event rate of 5.3% for moderate or worse severity COVID-19;

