### **6.13. Subgroup Analyses**

This study is not powered for subgroup analyses; therefore, all subgroup analyses will be treated as exploratory.

Subgroup analyses will be conducted for the primary and key secondary endpoints. Subgroups may include

- role within the facility (resident, staff)
- age group by role within the facility (residents  $<$  median resident age, residents  $\geq$  median resident age, staff  $<$  median staff age, staff  $\geq$  median staff age)
- sex (male, female)

- race
- ethnicity
- concomitant medication of interest use (yes/no)

Additionally, AEs, SAEs, and TEAEs will be summarized by role within the facility (resident vs staff).

For subgroup analyses, all tests of interactions between treatment groups and other factors will be conducted at a 2-sided alpha level of 0.10. Treatment group differences will not be evaluated within each category of the subgroup if the interaction is statistically significant. If any group within the subgroup is <10% of the total population, only summaries of the efficacy data will be provided, that is, no inferential testing.

The analysis of additional subgroups and/or subgroup analyses on additional endpoints will not require an amendment to the SAP.

Within each subgroup category the relevant summary measure by treatment, treatment differences (compared to placebo) and 95% CIs will be displayed. Also, p-values using appropriate statistical tests for treatment comparison will be provided. Forest plots may be generated to display the treatment difference and 95% CIs for selected efficacy subgroup analyses.

Concomitant therapies of interest include remdesivir, lopinavir/ritonavir, chloroquine, hydroxychloroquine, anticoagulants, or other investigational interventions. Details of the medications included in this subgroup are provided below in [Table PYAD.6.11](#). Other concomitant therapies of interest may be evaluated based on available external information.

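### SAP 6.13 bars within-category treatment comparisons when the interaction is significant, which is backwards and contradicts the same section's promise to show them

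*SAP*

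**What the plan says.** SAP 6.13 makes five statements that bear on this point.

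- Status: "This study is not powered for subgroup analyses; therefore, all subgroup analyses will be treated as exploratory".
- Interaction test: "For subgroup analyses, all tests of interactions between treatment groups and other factors will be conducted at a 2-sided alpha level of 0.10". Protocol 9.4 sets the same level.
- Restriction: "Treatment group differences will not be evaluated within each category of the subgroup if the interaction is statistically significant".
- Small categories: "If any group within the subgroup is <10% of the total population, only summaries of the efficacy data will be provided". The SAP explains this as no inferential testing.
- Presentation, in a later paragraph: "Within each subgroup category the relevant summary measure by treatment, treatment differences (compared to placebo) and 95% CIs will be displayed". The next sentence adds that "p-values using appropriate statistical tests for treatment comparison will be provided". Neither sentence mentions the interaction result.

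The section covers the primary and key secondary endpoints and lists factors that may be used: role in the facility, age group by role, sex, race, ethnicity and concomitant medication of interest. Protocol 9.4.7 names one subgroup analysis among its possible exploratory analyses: "subgroup analyses of primary and key secondary endpoints within residents versus staff". The protocol has no rule that withholds category results.

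**The concern.** An interaction test asks whether the treatment effect differs between categories. If it is not significant, the overall effect is a reasonable summary for each category. If it is significant, the overall effect may describe neither category well, and the reader needs the separate estimates. The restriction works the other way: it permits within-category evaluation when there is little sign of a difference and forbids it when there is a signal.

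The section also gives no way to decide between the restriction and the later unconditional paragraph. With a significant interaction, the analyst would have to choose which instruction to follow after seeing the interaction result, a choice that pre-specification is meant to remove. The choice could fall on resident versus staff. Role is a randomization stratification factor (Protocol 6.3, SAP 5.3.1), and the plan requires at least 300 residents because of their higher risk of a more severe course (Protocol 9.2, SAP 5.2).

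**Working it through.** **Step 1. Compare the instructions in SAP 6.13.**

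| Interaction result | Restriction sentence | Later paragraph | Can both be followed? |
|---|---|---|---|
| Not significant at 0.10 | Evaluation allowed | Differences, CIs, p-values given | Yes |
| Significant at 0.10 | Evaluation not done | Differences, CIs, p-values given | No |

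The conflict arises only in the second row, the informative case.

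**Step 2. Look for a correction elsewhere.** Protocol 9.4 repeats the 0.10 level without a restriction. Protocol 9.4.7 lists resident versus staff without one. SAP 6.1.4 allows further exploratory analyses but says nothing on this rule. Nothing in either document resolves the conflict.

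**Step 3. Illustrate how the restriction behaves.** The plan gives no figure for this, so the calculation shows direction only. It uses the Part 1 planning count: "For Part 1, an estimated 33 events are needed to show superiority" (SAP 5.2).

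Check of that count, with the Schoenfeld formula, 1:1 allocation, two-sided 0.05 and 90% power:

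- The placebo rate of 4.0% and risk ratio of 0.33 give an active rate of 1.32% and a hazard ratio of ln(1 − 0.0132)/ln(1 − 0.04) = 0.3255.
- Events = 4 × (1.960 + 1.282)² / (ln 0.3255)² = 42.03/1.260 = 33.4. This is 33 to the nearest integer, or 34 rounded up; power at 33 events is 0.897.
- With 0.33 used directly as the hazard ratio, the formula gives 35 events, and power at 33 is 0.890.

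The stated 33 is reproduced closely enough to use here.

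Chance that the interaction test is significant, by normal approximation:

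- In a category with d events and hazard ratio h, active events = d × h/(1 + h) and placebo events = d/(1 + h).
- The variance of the difference in log hazard ratios is the sum of 1/events over the four cells.
- θ = |ln(h₁/h₂)| / √variance.
- Chance = Φ(θ − 1.645) + Φ(−θ − 1.645).

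Worked case, 16.5 events per category, hazard ratios 0.20 and 0.60:

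- Cells are 2.75 and 13.75, and 6.19 and 10.31.
- Variance = 0.364 + 0.073 + 0.162 + 0.097 = 0.695; standard error 0.834.
- θ = 1.099/0.834 = 1.318.
- Chance = Φ(−0.327) + Φ(−2.963) = 0.372 + 0.002, about 37%.

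| Assumed hazard ratios | Restriction applies, equal split | First category has 30% to 70% of events |
|---|---|---|
| 0.33 and 0.33 | 10% | 10% |
| 0.20 and 0.60 | 37% | 31% to 37% |
| 0.20 and 1.0 | 62% | 52% to 62% |
| 0.15 and 1.5 | 83% | 72% to 83% |

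The further apart the true effects, the more often the restriction applies. The category hazard ratios and event splits are assumptions; neither document gives them.

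**The case against.** The strongest reply is that the results would be reported anyway. The later paragraph promises them without condition, the protocol contains no restriction, and SAP 6.13 lets further subgroup analyses be added without an amendment. A reader might infer from the restriction that category effects will be withheld and that only a pooled effect would remain. The documents do not support that inference: suppression is one side of a contradiction, and nothing says which side prevails. This part of the reply stands.

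A second reply is that evaluating means formal testing while displaying means description, so the two paragraphs are compatible. That would reconcile the differences and intervals. It fails on the p-values, because a within-category p-value is a test of the treatment difference.

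A third reply is that these analyses are exploratory and unpowered. That is right, and it limits the weight of the point. It does not make the instruction workable.

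Two further readings go beyond the text. A reader might call resident versus staff the trial's main subgroup question; it is the only subgroup analysis the protocol names, but it is listed among analyses that may be done and neither document ranks it. A reader might also multiply six factors by three endpoints to get 18 interaction tests per comparison. That count requires every optional factor to be used, and the 10% rule may remove some.

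**Conclusion.** The concern holds as a reversed rule and an internal contradiction in SAP 6.13. Followed literally, the restriction withholds within-category comparisons when they are most informative. Read with the rest of the section, it leaves the analyst with two incompatible instructions whenever an interaction reaches 0.10. This conclusion rests on the wording alone and needs no numerical assumption; the percentages in the illustration depend on assumed category effects and show direction only.

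The size is modest. The point touches exploratory subgroup analyses of the primary and key secondary endpoints. The primary and key secondary tests, the testing sequence in SAP 6.5 and the event targets do not change. Whether the restriction is a slip (a stray negative, or an intended statement that the interaction result does not matter) cannot be settled from the documents. The sentence needs correcting in either case.

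**What to change.** Replace the restriction sentence in SAP 6.13 with:

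> Treatment differences with 95% CIs (and p-values) will be presented within every category regardless of the interaction result, subject to the 10% rule on inferential testing; where the interaction p-value is below 0.10, within-category effects will be examined and interpreted as exploratory.

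The reference to the 10% rule is needed because the later paragraph's promise of p-values also carries no exception for small categories. The cost is one sentence in the SAP. No data collection, sample size or confirmatory analysis changes.

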**Table PYAD.6.11. Concomitant Medications of Interest Subgroup**

Drug name	ATC Code	ATC Preferred Term
Remdesivir	---	REMDESIVIR
Kaletra	J05AR	KALETRA
Lopinavir	J05AR	LOPINAVIR
Hydroxychloroquine	P01BA	HYDROCHLOROQUINE
Dexamethasone	R01AD	DEXAMETHASONE

**Concomitant Medications of Interest Subgroup**

Drug name	ATC Code	ATC Preferred Term
Chloroquine	P01BA	CHLOROQUINE
Baricitinib	L04AA	BARICITINIB
Heparin	B01AB	HEPARIN
Fondaparinux	B01AX	FONDIIPARINUX
Argatroban	B01AE	ARGATROBAN

Abbreviation: ATC = anatomical therapeutic chemical.

## 6.14. Protocol Violations

Protocol deviations will be identified throughout the study. Important protocol deviations (IPDs) are defined as those deviations from the protocol that would potentially compromise patients' safety, data integrity, or study outcome.

A separate document known as the "PYAD Trial Issues Management Plan" describes the categories and subcategories of IPDs and how the IPDs would be identified.

The number and percentage of patients having IPDs will be summarized within category and subcategory of deviations by dosing regimen.

A by-patient listing of IPDs will be provided.

## 6.15. Interim Analyses and Data Monitoring

### 6.15.1. Interim Analyses

Monitoring of unblinded safety data will occur throughout the study and will be conducted by an external Data and Safety Monitoring Board (DSMB). The DSMB will make recommendations concerning the conduct of the studies, including changes to the informed consent form.

The DSMB will review summary unblinded data monthly from the first participant entering treatment. Safety will be evaluated at each of these interim analyses and benefit/risk of LY3819253 will be assessed if needed.

The DSMB will review the following types of data:

- Demographics
- Baseline characteristics
- AEs
- SAEs
- Laboratory data
- PK/PD data (if available)
- Vital signs
- Concomitant medications

- Historical/pre-existing conditions
- Discontinuations
- Product complaints

The PYAD(c) study may be stopped early based on an unacceptable safety signal(s).

Only the DSMB is authorized to evaluate unblinded interim analyses and safety analyses. Study sites will receive information about interim results only if they need to know for the safety of their participants.

Further details regarding the interim analyses can be found in the DSMB Charter.

### **6.15.2. Data Monitoring Committee/Assessment Committee**

The sponsor will form a DSMB to analyze the interim study data. To minimize any bias introduced into the analysis of the study results, analysis plans will be finalized and approved prior to the interim analyses.

The primary goal of the DSMB is to review the interim results regarding the continuing safety of study participants and the continuing validity and scientific merit of the study. Information that may unblind the study during the analyses will not be reported to study sites or the blinded study team until the study has been unblinded.

Details of the DSMB will be provided in the DSMB charter. Unblinding details are specified in a separate blindind and unblinding plan document.

## **6.16. Additional Exploratory Analyses**

### **6.16.1. Protocol Defined Exploratory Endpoints**

Protocol defined exploratory endpoints are described in Section 4.3 and analysis details are provided in the following sections.

#### **6.16.1.1. Time to Improvement to Mild Severity Symptoms**

Time to improvement to mild severity symptoms will be is defined (in days) as:

*(Date when participant's symptoms first meet definition of mild severity – Date when participant's symptoms first meet definition of moderate or worse severity + 1)*

Only patients who have at baseline or later develop moderate-or-worse severity COVID-19 will be included in the analysis. If a patient has not experienced improvement to mild symptoms by completion or early discontinuation of the Evaluable Period, the patient will be censored at the date of their last visit during the Evaluation Period.

Time to improvement to mild severity symptoms will be summarized by treatment group and listed for the Prevention populations and the Part 1 Treatment population. In addition, a graphical presentation of the symptom improvement will be provided using a KM plot.

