The maximum total duration of study participation for each participant of the treatment group is 12 weeks. See the SOA for the treatment group in Section 1.3.2.

This table describes the visit types for the prevention population for this study.

Study Day	Activity	Visit Type
0,1	Follow SoA	Onsite
8, 15, 22, 29, 36, 43, 50, 57	Follow SoA Vital signs*	Onsite or Home (Virtual [record collection] if hospitalized)

Daily 2 - 57	Vital signs and symptoms questionnaire daily* Vital signs, clinical status, and concomitant procedures for hospitalized participants.	Onsite or Home (Virtual [record collection] if hospitalized)
ETV and follow-up (85, 141, 169)	Follow SoA	Onsite or Home

*Collected via direct data capture for onsite or home visits only.

This table describes the visit types for the treatment population for this study.

Study Day	Activity	Visit Type
0, 1	Follow SoA	Onsite
8, 29	Follow SoA Vital signs*	Onsite or Home (Virtual [record collection] if hospitalized)
Daily 2-29	Vital signs, clinical status, and concomitant procedures for hospitalized participants.	Virtual (record collection) if hospitalized
ETV and follow-up (85)	Follow SoA	Onsite or Home

*Collected via direct data capture for onsite or home visits only.

Hospitalization

If a participant is hospitalized, efforts will be made to retrieve hospital records and report procedures and assessments according to the SoA, as feasible.

Definitions for COVID-19 Severity

This table gives the definitions for COVID-19 severity of illness for those participants who are SARS-CoV-2 positive as determined by standard RT-PCR assay or equivalent test.

Table 1 Definitions for COVID-19 Severity

Severity	Description
Mild	Mild symptoms that could include: 
 fever, cough, sore throat, malaise, headache, muscle pain, gastrointestinal symptoms, without shortness of breath or dyspnea AND No clinical signs indicative of Moderate, Severe, or Critical Severity
Moderate	Symptoms of moderate illness with COVID-19, which could include any symptom of mild illness or shortness of breath with exertion AND Clinical signs suggestive of moderate illness with COVID-19, such as: 
 respiratory rate \geq 20 breaths per minute,

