### 4.3. Exploratory Objectives

**Table PYAD.4.3. Exploratory Objectives of Part 1 of Study J2X-MC-PYAD(c) in Participants Negative at Baseline for SARS-CoV-2 RT-PCR and Serology**

Objectives	Endpoints
Exploratory	
Compare time to improvement to mild severity symptoms in participants who develop moderate or worse severity a COVID-19	
 
Time to improvement to mild severitya.
 

Characterize COVID-19 illness and severity according to NIAID ordinal scale(s)	
 
Worst score on NIAID ordinal scale(s).
 

Characterize SARS-CoV-2 viral endpoints in those participants that become RT-PCR positive.	
 
Proportion of participants that achieve SARS-CoV-2 clearance within 1, 2, or 3 weeks of positive RT-PCR
 
Time to SARS-CoV-2 clearance
 

Characterize emergence of viral resistance to LY3819253	
 
Comparison from the first positive sample to at least the last positive sample in a subset of participants.
 

Compare the duration of hospitalization due to COVID-19	
 
Cumulative days of hospitalization in those who are hospitalized due to COVID-19.
 

Abbreviations: COVID-19 = coronavirus disease – 2019; NIAID = National Institute of Allergy and Infectious Diseases; RT-PCR = reverse transcription – polymerase chain reaction; SARS-CoV-2 = severe acute respiratory syndrome coronavirus 2.

a as defined in Table 1 of the protocol

**Table PYAD.4.4. Exploratory Objectives of Part 1 of Study J2X-MC-PYAD(c) in Participants Positive at Baseline for SARS-CoV-2 RT-PCR and Negative at Baseline for Serology**

Objectives	Endpoints
Exploratory	
Compare the incidence of moderate or worse severity COVID-19 in participants without moderate or worse severity a COVID-19 at baseline	
 
Cumulative incidence of moderate or worse severity COVID-19; defined as moderate or worse disease severitya within 21 days of baseline.
 

Compare the incidence of COVID-19 in participants who are asymptomatic a baseline.	
 
Cumulative incidence of COVID-19; defined as mild or worse disease severitya within 21 days of baseline
 

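### The time-to-improvement formula in SAP 6.16.1.1 does not require the mild date to follow moderate-or-worse onset, so an earlier mild day yields a zero or negative time (exploratory endpoint only)

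*SAP*

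**What the plan says.** SAP 6.16.1.1 defines the time in days as one date minus another, plus 1. The end date is the date on which the participant's "symptoms first meet definition of mild severity". The date subtracted, with the added day, is "Date when participant's symptoms first meet definition of moderate or worse severity + 1".

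The same section sets the analysis set: "Only patients who have at baseline or later develop moderate-or-worse severity COVID-19 will be included in the analysis". It also sets the censoring rule. It begins "If a patient has not experienced improvement to mild symptoms by completion or early discontinuation of the Evaluable Period", and such a patient is censored at the last visit in the Evaluation Period. Results are summarised by treatment group and "listed for the Prevention populations and the Part 1 Treatment population", with a Kaplan-Meier plot. No test or model is named for this endpoint.

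The objective in SAP 4.3, Table PYAD.4.3, is "Compare time to improvement to mild severity symptoms in participants who develop moderate or worse severity"; Protocol Section 3 has the same objective. Severity comes from Protocol Table 1 (Section 4.1.2). There, mild is a state judged on its own: mild symptoms, and "No clinical signs indicative of Moderate, Severe, or Critical Severity". Table 1 has no row for a participant without symptoms.

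**The concern.** Both dates are first dates, taken independently. If illness starts mild and worsens, the first mild date lies before the first moderate date, and the formula picks it up. The result then reflects the interval before worsening, with its sign reversed, and says nothing about recovery.

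The planned data can produce this pattern. The schedule for Part 1 and the Part 2 Prevention Cohort (Protocol 1.3.1, and the visit table in 4.1.2) collects symptoms and vital signs daily through Day 57, so a mild day before progression would be recorded. SAP 6.10.3.1 itself has a sensitivity analysis for participants who develop COVID-19 and later reach moderate-or-worse disease.

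At stake is the between-arm description of recovery. Values of zero or less have no sensible place on a Kaplan-Meier curve of recovery time, and some participants would be given the wrong event status.

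**Working it through.** The documents give no figure for this endpoint, so there is none to reproduce. The check applies the formula to example severity courses.

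**Inputs**
- M = first date mild is met; W = first date moderate or worse is met (SAP 6.16.1.1).
- Severity states as in Protocol Table 1.
- Example course (assumed): moderate from Day 14, mild again on Day 20. The participant is taken to be classifiable under Table 1, that is SARS-CoV-2 positive, on every day used.

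**Formula as written:** T = M - W + 1. If the first mild day is L days before moderate onset, M = W - L, so T = 1 - L.

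**Formula with the order stated:** T* = M* - W + 1, where M* is the first mild date after W. Here T* = 20 - 14 + 1 = 7, whatever happened before Day 14.

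| Earlier mild day | As written | Order stated |
|---|---|---|
| none | 20 - 14 + 1 = 7 | 7 |
| Day 13 (L = 1) | 13 - 14 + 1 = 0 | 7 |
| Day 12 (L = 2) | 12 - 14 + 1 = -1 | 7 |
| Day 11 (L = 3) | 11 - 14 + 1 = -2 | 7 |
| Day 10 (L = 4) | 10 - 14 + 1 = -3 | 7 |
| Day 7 (L = 7) | 7 - 14 + 1 = -6 | 7 |

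**Other courses**
- *Never improves.* Mild on Day 11, moderate from Day 14 to the end. As written, 11 - 14 + 1 = -2, with an event date available. With the order stated there is no M*, so the participant is censored. Here the SAP's formula and its own censoring sentence point in different directions.
- *Moderate at baseline.* Moderate on Day 1, mild on Day 8, no earlier mild day. Both versions give 8 - 1 + 1 = 8.
- *Moderate straight to no symptoms.* Moderate Days 14 to 19, none from Day 20. Table 1 mild needs mild symptoms, so no mild date exists and the participant is censored under both versions. Stating the order does not cure this. Counting mild or better gives 20 - 14 + 1 = 7.

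**The case against.** The strongest reply is that the intended order is plain. The section heading speaks of improvement, only participants with moderate-or-worse disease enter, and censoring applies to those who have not improved. A mild day before moderate illness is not an improvement. On this view the formula is shorthand with a missing qualifier, and negative durations would be noticed when the plot is programmed. SAP 6.16.1.4 is drafted in the same way (first negative test minus first positive test), although Prevention participants are RT-PCR negative at baseline.

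This stands as evidence of intent. It does not rescue the formula, which is the text that gets programmed. Nor does the stated intent settle how a direct move from moderate to no symptoms counts. Finding the same habit in 6.16.1.4 is a reason to write the order down.

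It can also be said that counting no symptoms as an event goes beyond the protocol's wording, which names improvement to mild severity. That is fair, so the choice should be explicit. Still, a participant without symptoms has improved at least that far.

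A reader might infer more: that mild illness usually comes first, so typical cases have negative times; that the analysis fails for anyone who progressed; or that the fastest recoveries are lost. The documents do not support these. They give no frequency for an earlier mild day. Table 1 lets moderate be the first state met, because any mild symptom plus a sign such as a heart rate of 90 or more is enough. Moderate-to-severe progression with no earlier mild day is unaffected. Nothing shows that a direct move to no symptoms is common or especially fast.

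**Conclusion.** The formula is wrong as written, for an exploratory endpoint only. A participant with a recorded mild day L days before first moderate-or-worse severity gets 1 - L days in place of the time to recovery: zero at L = 1 and negative from L = 2. Such a participant who never improves can be counted as improved. Separately, a direct move from moderate to no symptoms is censored under the literal wording.

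The share affected is not given. Among participants who become moderate or worse after baseline it could lie anywhere from 0 to 100%. The ordering fault leaves participants with no earlier mild day, including those moderate at baseline, with the correct value. The conclusion assumes that the formula is programmed literally; a programmer who follows the heading and the censoring sentence would avoid the ordering error but not the no-symptoms gap. Primary and key secondary endpoints, and the testing scheme in SAP 6.5, do not use this quantity.

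**What to change.** In SAP 6.16.1.1, define the event date as the first date after first moderate-or-worse onset on which severity is mild or better, including no symptoms. The time is that date minus the onset date, plus 1. Censor participants with no such date at their last Evaluation Period visit, as the section already provides. State that mild days before onset are ignored.

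The cost is one definition in the SAP. Data collection, sample size and the main analyses stay as they are. The date order in SAP 6.16.1.4 could be made explicit in the same edit.
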